#### 11.1.4 Relatedness

AEs will be categorized according to the likelihood that they are related to the study drug(s). Specifically, they will be categorized using the following terms:

Unrelated	Adverse Event is not related to the study drug(s)
-----------	---

Unlikely	Adverse Event is doubtfully related to the study drug(s)
Possible	Adverse Event may be related to the study drug(s)
Probable	Adverse Event is likely related to the study drug(s)
Definite	Adverse Event is clearly related to the study drug(s)

#### 11.1.5 An adverse event of special interest (AESI)

An adverse event of special interest (AESI) is one of scientific and medical interest specific to understanding of durvalumab and may require close monitoring. An AESI may be serious or non-serious.

AESIs observed with durvalumab include:

- Diarrhea/Colitis and intestinal perforation
- Pneumonitis/ILD
  - If new or worsening pulmonary symptoms (e.g., dyspnea) or radiological abnormality suggestive of pneumonitis/ILD is observed, toxicity management as described in detail in the Dosing Modification and Toxicity Management Guidelines (see Appendix A) will be applied. The results of the full diagnostic workup (including high-resolution computed tomography [HRCT], blood and sputum culture, hematological parameters, etc.) will be captured in the eCRF. It is strongly recommended to perform a full diagnostic workup, to exclude alternative causes such as lymphangitic carcinomatosis, infection, allergy, cardiogenic edema, or pulmonary hemorrhage. In the presence of confirmatory HRCT scans where other causes of respiratory symptoms have been excluded, a diagnosis of pneumonitis (ILD) should be considered and the Dosing Modification and Toxicity Management Guidelines should be followed.
  - The sponsor-investigator is responsible for ensuring that all staff involved in the study is familiar with the content of this section.
- hepatitis/transaminase increases
- Endocrinopathies (i.e. events of hypophysitis/hypopituitarism, adrenal insufficiency, hyper- and hypothyroidism and type I diabetes mellitus)
- Rash/Dermatitis
- Nephritis/Blood creatinine increases
- Pancreatitis/serum lipase and amylase increases
- Myocarditis
- Myositis/Polymyositis
- Neuropathy/neuromuscular toxicity (e.g. Guillain-Barré, and myasthenia gravis)
- Other inflammatory responses that are rare / less frequent with a potential immunemediated etiology include, but are not limited to, pericarditis, sarcoidosis, uveitis and other events involving the eye, skin, hematological and rheumatological events, vasculitis, non-infectious meningitis and non-infectious encephalitis.
- In addition, infusion-related reactions and hypersensitivity/anaphylactic reactions with a different underlying pharmacological etiology are also considered AESIs.

#### 11.1.6 Death

- Death due to disease progression should not be reported as a SAE, unless it is attributable by the site investigator to the study drug(s).
- Where death is not due (or not clearly due) to progression of the disease under study, the AE causing the death must be reported to HCRN as an SAE as described below. It should also be documented in the EDC system. The report should contain a comment regarding the co involvement of PD, if appropriate, and should assign main and contributory causes of death.
- Deaths with an unknown cause should always be reported as an SAE. It should also be documented in the EDC system. A post mortem may be helpful in the assessment of the cause of death, and if performed, a copy of the post-mortem results should be forwarded to AstraZeneca Patient Safety.
- Deaths occurring after the protocol defined safety follow up period after the administration of the last dose of study drug should be documented in the EDC system. If the death occurred as a result of an event that started after the defined safety follow up period and the event is considered to be due to a late onset toxicity to study drug, then it should also be reported as an SAE. AstraZeneca retains the right to request additional information for any patient with ongoing AE(s)/SAE(s) at the end of the study, if judged necessary.

#### 11.1.7 Overdose

An overdose is defined as a patient receiving a dose of durvalumab in excess of that specified in the Investigator's Brochure, unless otherwise specified in this protocol. Any overdose of a study patient with durvalumab, with or without associated AEs/SAEs, is required to be reported as a SAE to HCRN who will report to the sponsor-investigator. HCRN must report these to AstraZeneca Patient Safety as outlined in Section 11.2.2.2 within 7 calendar days. If the overdose results in an AE, the AE must also be recorded as an AE. Overdose does not automatically make an AE serious, but if the consequences of the overdose are serious, for example death or hospitalization, the event is serious and must be recorded and reported as an SAE. There is currently no specific treatment in the event of an overdose of durvalumab. The investigator will use clinical judgment to treat any overdose.

#### 11.1.8 Hepatic function abnormality

Hepatic function abnormality that fulfills the biochemical criteria of a potential Hy's Law case in a study patient, with or without associated clinical manifestations, is required to be reported as "hepatic function abnormal" as a SAE to HCRN who will report to the sponsor-investigator. HCRN must report these events to AstraZeneca Patient Safety within 7 calendar days, unless a definitive underlying diagnosis for the abnormality (e.g., cholelithiasis or bile duct obstruction) that is unrelated to investigational product has been confirmed. The criteria for a potential Hy's Law case is Aspartate Aminotransferase (AST) or Alanine Aminotransferase (ALT)  $\geq 3$  x Upper Limit of Normal (ULN) together with Total Bilirubin (TBL)  $\geq 2$  xULN at any point during the study following the start of study medication irrespective of an increase in Alkaline Phosphatase (ALP).

- If the definitive underlying diagnosis for the abnormality has been established and is unrelated to investigational product, the decision to continue dosing of the study patient will be based on the clinical judgment of the investigator.
- If no definitive underlying diagnosis for the abnormality is established, dosing of the study patient must be interrupted immediately. Follow-up investigations and inquiries must be initiated by the investigational site without delay.

Each reported event of hepatic function abnormality will be followed by the site investigator and evaluated by the sponsor-investigator and AstraZeneca.

### 11.1.9 Pregnancy

#### 11.1.9.1 Maternal exposure

If a patient becomes pregnant during the course of the study, durvalumab should be discontinued immediately. Pregnancy itself is not regarded as an AE unless there is a suspicion that durvalumab may have interfered with the effectiveness of a contraceptive medication.

Congenital abnormalities or birth defects and spontaneous miscarriages should be reported and handled as SAEs. Elective abortions without complications should not be handled as AEs. The outcome of all pregnancies (spontaneous miscarriage, elective termination, ectopic pregnancy, normal birth, or congenital abnormality) should be followed up and documented even if the patient was discontinued from the study. If any pregnancy occurs in the course of the study, then the site investigator or other site personnel should inform HCRN within 1 business day and HCRN will report to the sponsor-investigator. HCRN will work with the site investigator to ensure that all relevant information is provided within 1 to 5 calendar days. HCRN must report to AstraZeneca Patient Safety within 7 calendar days for pregnancies with SAEs and within 30 days for all other pregnancies. The same timelines apply when outcome information is available.

#### 11.1.9.2 Paternal exposure

Pregnancy of the patient's partner is not considered to be an AE. However, the outcome of all pregnancies (spontaneous miscarriage, elective termination, ectopic pregnancy, normal birth, or congenital abnormality) occurring from the date of the first dose until 180 days after the last dose of durvalumab, should, if possible, be followed up and documented.

## 11.2 Reporting

### 11.2.1 Adverse Events

- AEs will be recorded from time of signed informed consent until 90 days after discontinuation of study drug(s) or until a new anti-cancer treatment starts, whichever occurs first.
- AEs will be recorded regardless of whether or not they are considered related to the study drug(s).
- All AEs will be recorded in the subject's medical record and on the appropriate study specific eCRF form within the EDC system.

- AEs considered related to study drug(s) will be followed until resolution to  $\leq$  Grade 1 or baseline, deemed clinically insignificant, and/or until a new anti-cancer treatment starts, whichever occurs first.

### 11.2.2 Serious Adverse Events (SAEs)

#### 11.2.2.1 Site Requirements for Reporting SAEs to HCRN

- SAEs will be reported from time of signed informed consent until 90 days after discontinuation of study drug(s) or until a new anti-cancer treatment starts, whichever occurs first.
- SAEs will be reported on the SAE Submission Form within 1 business day of discovery of the event.
- SAEs include events related and unrelated to the study drug(s).
- All SAEs will be recorded in the subject's medical record and on the appropriate study specific eCRF form within the EDC system.
- All SAEs regardless of relation to study drug will be followed until resolution to  $\leq$  Grade 1 or baseline and/or deemed clinically insignificant and/or until a new anti-cancer treatment starts, whichever occurs first.

The site will submit the completed SAE Submission Form to HCRN within 1 business day of discovery of the event. The form may be submitted to HCRN electronically to [[contact]](mailto:[contact]). The site investigator is responsible for informing the IRB and/or other local regulatory bodies as per local requirements.

The original copy of the SAE Submission Form and the email correspondence must be kept within the study file at the study site.

Once the SAE has resolved (see resolution guidelines listed above), sites must submit a followup SAE Submission Form within a reasonable timeframe to HCRN electronically to [[contact]](mailto:[contact]).

#### 11.2.2.2 HCRN Requirements for Reporting SAEs to AstraZeneca

HCRN will report all SAEs to AstraZeneca within 1 business day of receipt of the SAE Submission Form from a site. Follow-up information will be provided to AstraZeneca as it is received from site. All SAE correspondence should be sent to AstraZeneca via the following address: [[contact]](mailto:[contact]).

### 11.3 Sponsor-Investigator Responsibilities

HCRN will send a SAE summary to the sponsor-investigator within 1 business day of receipt of SAE Submission Form from a site. The sponsor-investigator will promptly review the SAE summary and assess for expectedness and relatedness.

### 11.4 HCRN Responsibilities to FDA

For protocols exempt from the requirements of an IND, HCRN will continue to facilitate compliance of applicable requirements for the sponsor-investigator in relation to this study. This

includes but is not limited to 21 CFR 50.20 informed consent, 21 CFR Part 56 IRB, and pertinent sections of the Public Health Service Act and FDAAA.

#### 11.5 IND Safety Reports Unrelated to this Trial

AstraZeneca will provide to HCRN IND safety reports from external studies that involve the study drug(s) per their guidelines. HCRN will forward safety reports to the sponsor-investigator who will review these reports and determine if revisions are needed to the protocol or consent. HCRN will forward these reports to participating sites within 1 business day of receiving the sponsor-investigator's review. Based on the sponsor-investigator's review, applicable changes will be made to the protocol and informed consent document (if required). All IND safety reports will also be made available to sites via the EDC system.

Upon receipt from HCRN, site investigators (or designees) are responsible for submitting these safety reports to their respective IRBs, as per their IRB policies.

### 12. STATISTICAL METHODS

#### 12.1 Study Design

This is a single arm study of induction durvalumab (1500 mg IV) for 1 cycle (every 4 weeks), administered prior to starting concurrent definitive chemoradiation, followed by consolidation durvalumab (1500 mg IV every 4 weeks) for up to 12 cycles.

#### 12.2 Endpoints

##### 12.2.1 Definition of Primary Endpoint

1. Estimate 12-month progression-free survival (PFS) in patients with Stage III non-small cell lung cancer (NSCLC). Compare with PACIFIC trial 12-month progression-free survival as historical control. In the PACIFIC study, 12-month progression-free survival was 55.9% and was measured using baseline imaging from the time of patient randomization after completion of chemoradiation (1-42 days after completion of chemoradiation). For this study, in order to allow for comparison with this historical control, 12-month PFS will be measured starting at imaging performed 1-42 days after completion of chemoradiation, prior to initiation of consolidation durvalumab.
2. Assess the safety and feasibility of induction durvalumab followed by chemoradiation and consolidation durvalumab for stage III NSCLC. Toxicity will be measured and recorded as defined by the NCI Common Terminology Criteria for Adverse Events (NCI CTCAE) v5.

Patients receiving different chemotherapeutic agents will be analyzed together for toxicity, with exploratory analysis of toxicity related to different chemotherapeutic regimens.

##### 12.2.2 Definition of Secondary Endpoints

1. Objective response rate (ORR). ORR will be measured using two timepoints, using RECIST 1.1. "ORR1" will be assessed after completion of induction and chemoradiation

in comparison with baseline imaging. “ORR2” will also be assessed comparing first imaging after completion of induction and chemoradiation to imaging after consolidation durvalumab.

#### 12.2.3 Correlative/Exploratory Endpoints

Data analysis for the correlative/exploratory objectives are descriptive and exploratory. Refer to Sections 12.6.3 and 12.6.5, below, for details of analysis plan for the correlative and exploratory endpoints.

- Correlation of outcomes and toxicity based upon tumor and immune cell PD-L1 status in baseline tumor biopsy prior to therapy.
- Correlation of toxicity based upon type of chemotherapy administered.

Patients receiving different chemotherapeutic agents will be analyzed together for toxicity, with exploratory analysis of toxicity related to different chemotherapeutic regimens.

- Correlation of outcomes based upon tumor mutation burden in baseline tumor biopsy prior to therapy
- Assessment of immune response via peripheral blood immune monitoring through multiple timepoints of therapy
- Correlation of immune response with outcomes in terms of disease control and toxicity
- Correlation of tumor immune score via quantitative multiplex tumor biopsy assay with clinical outcomes
- Exploration of immune response signal to indicate further exploration of a treatment schedule in a larger trial
- Collection of microbiome samples to correlate with outcomes and toxicity

#### 12.3 Sample Size and Accrual

This study will be planned to detect a 14% improvement in 12-month progression-free survival as a potential signal to move forward with further evaluation in a large randomized trial. Thus, 12-month progression-free survival of 69.9% would be felt to be clinically meaningful for further investigation.

Assuming that 12-month PFS in the historical control group is 55.9%, with an 18-month accrual interval and additional 12-month follow up after the accrual interval, the required sample size would be 49 patients, with a one-sided test given type I error 0.05 and power of 0.8.

Accounting for a 10% dropout rate, a total of 54 patients would be enrolled in this study.

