## SCHEMA

## 1. BACKGROUND AND RATIONALE

### 1.1 Non-Small Cell Lung Cancer Background

Non-small cell lung cancer (NSCLC) is the most common cancer killer in the United States, and worldwide. Despite indications of benefit of low dose CT screening for lung cancer in certain high-risk populations, most patients with NSCLC are diagnosed at more advanced stages. The majority of patients with stage III NSCLC are not eligible for surgical resection, and despite curative-intent treatment with definitive chemoradiation, most will experience disease recurrence and will die.

In a randomized phase III trial evaluating the addition of consolidation durvalumab after completion of standard of care concurrent platinum-doublet chemotherapy with radiation for patients with stage III NSCLC, progression-free survival (PFS) was significantly improved with durvalumab compared with placebo (16.8 months vs 5.6 months;  $P<0.001$ ). This benefit, including a benefit of 12-month and 18-month PFS, was demonstrated across all subgroups, and was independent of PD-L1 tumor expression prior to chemoradiation. Median time to death or development of metastasis was significantly improved with durvalumab compared with placebo (23.2 months vs 14.6 months), and fewer patients receiving durvalumab developed brain metastases (5.5% vs 11%). Objective response rate was significantly improved with durvalumab (28.4% vs 16%) (1). Overall survival was also significantly improved with durvalumab (hazard ratio for death, 0.68; median overall survival with durvalumab not reached, versus 28.7 months with placebo) (2). Despite prior concerns regarding potential increased risk of pneumonitis with checkpoint inhibition after radiation, no significant difference in grade 3 or 4 pneumonitis was seen with durvalumab, although an expected increase in immune-mediated adverse events was seen with durvalumab compared with placebo (24.2% vs 8.1%, respectively) (1).

Nivolumab has been evaluated as neoadjuvant therapy for resectable stage IB-IIIA NSCLC in a small feasibility study (3). Nivolumab, 3 mg/kg every 2 weeks, was administered for 2 doses prior to surgical resection in 22 patients. Twenty patients underwent surgical resection (1 patient withdrew without toxicity or disease progression; 1 patient had unresectable disease).

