## 12.6 Data Analysis Plans

### 12.6.1 Analysis Plans for Primary Objective

The progression-free survival analyses will be performed considering the risk of dying from another cause before experiencing progression related events using the competing risk egression method (de Glas et al., 2016). Cumulative incidence functions will be displayed and summarized for the median time to progression as well as percentage of progression patients at 12, 18, and 24 months. In addition, competing risk regression will be used to estimate sub distribution hazard ratios of the study arm versus historical control arm and 95% confidence intervals, adjusted for patient demographic, clinical, pathological, and tumor related factors. To compare the overall survival between groups, Kaplan-Meier survival curves will be displayed and summarized. Survival curves will be statistically compared using the log-rank test. If the proportional hazards assumption is met, survival curves will also be compared using proportional Cox regression, adjusting for risk factors.

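### N = 49, one-sided alpha 0.05 and power 0.80 do not hold together: 49 reproduces with an exponential benchmark curve and events to month 30, and the protocol's own benchmark median does not fit that curve

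*Combined protocol and SAP*

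**What the plan says.** Section 12.3 and the Synopsis take 55.9% as the benchmark 12-month PFS. Section 12.3 adds that "12-month progression-free survival of 69.9% would be felt to be clinically meaningful for further investigation". The calculation is made "with an 18-month accrual interval and additional 12-month follow up after the accrual interval", and "the required sample size would be 49 patients", "with a one-sided test given type I error 0.05 and power of 0.8". Neither place names the test or the survival distribution.

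Section 1.1 reports the benchmark trial's median PFS, durvalumab against placebo, as "16.8 months vs 5.6 months".

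The sections differ on how long PFS is observed:

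- Section 12.6.1 plans to report the "percentage of progression patients at 12, 18, and 24 months" and to compare with the historical control by competing-risk regression. It gives no one-sample test, critical value or decision rule.
- Section 9.8.8 measures PFS over the 12 months after consolidation starts.
- Section 7, footnote 12, follows patients who stop treatment without progression only until 12 months after consolidation starts.

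**The concern.** A test of 12-month status needs one benchmark number and no curve shape, and an accrual period would not enter its sample size. Listing 18 months of accrual and 12 months of further follow-up as inputs suggests a calculation that counts events between months 12 and 30 under an assumed curve. If the assumed curve falls faster after month 12 than the benchmark really does, the null expects too many late events. A regimen no better than the benchmark then looks better than it.

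The trial's declared purpose is a signal for moving to a large randomized trial. What is at stake is whether the 5% false-positive rate and 80% power attached to that signal are correct.

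**Working it through.** **Inputs.** From Section 12.3: p0 = 0.559, p1 = 0.699, one-sided alpha 0.05 (z = 1.645), power 0.80 (z = 0.842), accrual 18 months, further follow-up 12 months. From Section 1.1: benchmark median 16.8 months. Assumption: uniform entry, so follow-up is 12–30 months per patient.

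**Step 1: reproduce 49.** With exponential curves, λ0 = −ln(0.559)/12 = 0.0485 and λ1 = −ln(0.699)/12 = 0.0298 per month, a hazard ratio of 0.616. The probability of an event during follow-up is P(λ) = 1 − (e^(−12λ) − e^(−30λ))/(18λ), which gives P0 = 0.627 and P1 = 0.459.

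- One-sample log-rank: v1 = P1 = 0.459 and v0 = 0.459/0.616 = 0.746. N = (1.645√v0 + 0.842√v1)²/(v0 − v1)² = 48.3, so 49.
- Exponential hazard on the cube-root scale: N = {[1.645 λ0^(1/3)/(3√P0) + 0.842 λ1^(1/3)/(3√P1)] / (λ0^(1/3) − λ1^(1/3))}² = 48.98, so 49.
- Other exponential variants give 47–58.

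Methods that use only 12-month status do not reach 49. The normal binomial formula gives (1.645√(0.559×0.441) + 0.842√(0.699×0.301))²/0.14² = 73.8, so 74. The exact binomial gives 79. The remaining landmark methods tried (arcsine, log and complementary log-log scales, alternative variance only, log-rank cut at month 12) fall between 67 and 82.

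**Step 2: compare that curve with the protocol's benchmark.** An exponential through 55.9% at 12 months has median ln 2/0.0485 = 14.3 months, not 16.8. An exponential with median 16.8 has 12-month PFS 0.5^(12/16.8) = 61.0%, not 55.9%. Taken together, the two figures imply an average hazard of 0.0485 per month to month 12 and ln(0.559/0.5)/4.8 = 0.0232 per month from month 12 to 16.8, about half.

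**Step 3: type I error at n = 49 against the exponential null.** The true curve passes through both benchmark figures, so there is no benefit. Each cell rests on 100,000 simulated trials. Entries are the standard / modified one-sample log-rank, which reject when (E − O)/√E or (E − O)/√((E + O)/2) exceeds 1.645.

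| True benchmark curve | Follow-up 12–30 months | Time zero 3.5 months after registration (assumed; 8.5–26.5 months) | PFS cut at 12 months |
|---|---|---|---|
| Exponential (check) | 0.041 / 0.053 | 0.042 / 0.055 | 0.041 / 0.057 |
| Weibull, shape 0.52 | 0.189 / 0.222 | 0.106 / 0.129 | 0.022 / 0.032 |
| Hazard stays at 0.0232 after month 12 | 0.245 / 0.283 | 0.162 / 0.195 | 0.040 / 0.055 |
| Hazard back to 0.0485 after month 16.8 | 0.112 / 0.136 | 0.096 / 0.120 | 0.041 / 0.057 |
| Rejoins the exponential at month 30 (contrived floor) | 0.083 / 0.103 | 0.080 / 0.101 | 0.041 / 0.055 |

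The cube-root test behaves alike over 12–30 months: 0.048 under a true exponential, 0.274 with the lower hazard continuing, 0.128 with the return to 0.0485.

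**Step 4: power at n = 49.**

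- PFS cut at 12 months: log-rank 0.62 (standard) to 0.68 (modified). The exact binomial rejects at 34 or more of 49 progression-free, with alpha 0.038 and power 0.60. At 33 its alpha would be 0.069.
- Events to month 30, tested against the correct curve: alpha returns to 0.04–0.055. Power is 0.70–0.76 for the Weibull and constant-lower-hazard curves, for which power 0.80 needs N of about 54–64.

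**The case against.** The strongest case against is that type I error belongs to a test, and the plan names no test against an exponential curve. Section 12.6.1 lists competing-risk regression, Kaplan-Meier, log-rank and Cox methods, and a model used for sizing does not bind the analysis. Nor does the calendar provide for follow-up to month 30. Scans are scheduled during consolidation, whose twelve four-week cycles end at about month 11, and progression follow-up after stopping treatment ends at month 12. The only support for later data is the reporting of 18- and 24-month percentages, which is descriptive.

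This stands. A reader might infer that the planned trial will pass an ineffective regimen in up to 28% of cases. The documents do not support that: the figure needs an inferred test, full 12–30 month follow-up, and an assumed curve after month 16.8, which the protocol does not give.

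Three narrower objections also stand:

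- A reader might say that the benchmark figures rule out an exponential curve. They are two point estimates without confidence intervals, so the misfit is one of stated values, not a formal rejection.
- A reader might say that 49 requires an exponential curve. The contrived floor curve, tested correctly with the modified log-rank, also gives about 49 and power 0.80. The curve whose hazard returns to 0.0485 comes close, with power 0.75–0.79.
- Twelve months after the last entry is also roughly what a landmark analysis needs for the last patient, so that input alone does not prove that later events were counted. The stronger evidence is that landmark methods give 67–82.

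None of this rescues the stated figures. Cutting PFS at month 12 removes the inflation but leaves power of 0.60–0.68.

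**Conclusion.** Wrong as written. N = 49, alpha 0.05 and power 0.80 reproduce on an exponential benchmark curve with events to month 30, and that curve's median (14.3 months) disagrees with the protocol's own 16.8 months.

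- If the sizing calculation is also the test and follow-up runs 12–30 months, the false-positive rate is about 11–28% over three plausible curves through both benchmark figures. It is 9.6–19.5% with an assumed 3.5-month lag before time zero, and about 8% at the contrived floor.
- If PFS is cut at 12 months, type I error is near nominal (about 2–6%) and the shortfall is in power.

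Which reading applies cannot be settled from the documents, because the test is unnamed and Sections 7, 9.8.8, 12.3 and 12.6.1 do not agree on the PFS window. On neither reading do the three figures hold together.

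**What to change.** In Sections 12.3 and 12.6.1 and the Synopsis:

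1. Make the primary test a 12-month landmark test against 55.9%, either the 12-month Kaplan-Meier estimate or an exact binomial. It needs no curve shape. State the critical value.
2. Restate alpha and power at the planned size. For the exact test at 49 this is 34 or more progression-free, alpha about 0.04, power about 0.60.
3. If later events are to count, test against a benchmark curve through both stated points (55.9% at 12 months, 50% at 16.8 months). State the shape assumed beyond them and restate power, about 0.70–0.76 at 49 for the Weibull and constant-lower-hazard curves.
4. Reconcile the PFS window across Section 7 (footnote 12), 9.8.8, 12.3 and 12.6.1.

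The cost is a recalculation and a short rewrite. The stated power falls clearly below 0.80. No extra patients are needed if the figure is restated. Restoring 0.80 would take about 67–82 evaluable patients on the landmark, or about 54–64 against the two non-exponential curves named in item 3.
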